**Figure 2: Study protocol for Phase 2**

**Table 2: Phase 2**

Goal 2-4: Develop, pilot test and evaluate the toolkit/intervention	
Stages/Goals	Goals and Activities
Goal 2	Toolkit refinement/Intervention development Co-designed strategies/toolkit from phase 1 will be compiled in the user-friendly intervention protocol for implementation
Goal 3	Intervention pilot test Recruitment of 25 participants meeting eligibility criteria Baseline survey data collection on the same measures used in Phase 1, Stage 2 Initiation of co-designed symptom-management intervention pre-discharge with telephone follow-up (symptom burden will be assessed at each follow-up) Survey data collection, at the end of the intervention (i.e., 6 weeks) and at 3 months after completion of the intervention
Goal 4	Intervention evaluation Participants survey and interview on satisfaction, feasibility, and acceptability of the intervention Data analysis
Dissemination	Manuscripts and project summary Dissemination at professional organization R01 Randomized Control Trial planning for scalability of the intervention

*Year 2 Goal 2:* The user-friendly intervention protocol will be developed by refining the symptom management toolkit established in Phase 1. The intervention will be nurse-driven person-centered pre-discharge intervention engaging caregivers followed by telephone support, which will focus on the management of symptoms such as difficulty breathing, pain, fatigue and sleep disturbances among critically ill patients with multimorbidity and as identified from the survey on symptom burden.

*Year 2 Goal 3:* We will pilot test the intervention among 25 participants over 9 month's local rollout period. The symptom management intervention will be delivered by a nurse pre-discharge with telephone follow up over a 6 weeks period (at 48 hrs, 1 week, 4 weeks and 6 weeks) after the discharge from JHH-IMCU.

*Year 2 Goal 4:* We will evaluate the effectiveness of the intervention on primary outcomes (i.e., symptom burden and QOL) by comparing pre-post intervention data (i.e., baseline, 6 weeks and 3 months). Additionally, the intervention is anticipated to improve secondary outcomes (i.e., pain, fatigue, social support, resilience, and healthcare utilization). To evaluate the acceptability and feasibility of the intervention both quantitative (survey items on satisfaction and acceptability, no. of nurse-patient contacts, recruitment rate and retention rate) and qualitative (unstructured interview with selected participants who attended the intervention and the nurse delivering the intervention) data will be examined.

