# Statistical Analysis Plan

- a. Primary outcome variable.
  - Symptom Burden: Edmonton Symptom Assessment System (ESAS)
  - Quality of Life: BRICS NINR Short Form Survey (SF-36)
- b. Secondary outcome variables.
  - Health-care Utilization: No. of emergency visit, Hospitalizations, Critical care admissions
- c. Statistical plan including sample size justification and interim data analysis.

Data collection and analysis are iterative processes throughout Goal 1, Stages 1-6 of the EBCD process, and Goal 3 and Goal 4 for intervention evaluation. The majority of data collected in phase 1, except the baseline survey, are qualitative and will be analyzed using thematic analysis. The software Atlas ti. will support qualitative analysis.

Quantitative data will be analyzed using descriptive statistics followed by inferential statistics. As a pilot study, the analyses of Phase 2 data will likely not have adequate power to detect significant differences. Therefore, effect sizes, followed by statistical significance will be explored for evidence of the effectiveness of the intervention on outcomes. To compare quantitative data at different time points, we will use Wilcoxon signed rank test to evaluate changes from baseline to 6 weeks and baseline to 3 months post-intervention. Additionally, the changes across baseline, 6 weeks, and 3 months post-intervention will be analyzed using the Friedman test for repeated measures, with Kendall's W employed to assess effect size.

Quantitative analyses will be performed using the Statistical Package for the Social Sciences (SPSS) or equivalent software. We will evaluate the acceptability and feasibility of the intervention using qualitative analysis of interview data from selected participants who attended the intervention, left the intervention if agree to interviewed and the nurse delivering the intervention. The quantitative data from satisfaction and feasibility items will be descriptively analyzed (mean, range, percentages). Further, evaluation of participants' recruitment rate, retention rate and no. of nurse patient interaction will be performed.

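### Phase 2 claims to evaluate effectiveness from before-after change in a single treated group, a design that can describe change but cannot attribute it to the intervention

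*Combined protocol and SAP*

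**What the plan says.** Section 4 of the protocol describes Phase 2 as a quasi-experimental pre-post study. Under Year 2 Goal 3: "We will pilot test the intervention among 25 participants". Table 2 (Goal 3) lists a baseline survey and then "Initiation of co-designed symptom-management intervention pre-discharge with telephone follow-up". The later surveys are set out as "Survey data collection, at the end of the intervention (i.e., 6 weeks) and at 3 months after completion of the intervention".

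Year 2 Goal 4 gives the purpose of the analysis: "We will evaluate the effectiveness of the intervention on primary outcomes (i.e., symptom burden and QOL) by comparing pre-post intervention data".

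SAP section c gives the analysis and how it will be read. For pairs of time points, "we will use Wilcoxon signed rank test to evaluate changes from baseline to 6 weeks and baseline to 3 months post-intervention". Change over all three time points is to be "analyzed using the Friedman test for repeated measures", with Kendall's W as the effect size. The SAP warns that "the analyses of Phase 2 data will likely not have adequate power to detect significant differences", and concludes from this that "effect sizes, followed by statistical significance will be explored for evidence of the effectiveness of the intervention on outcomes".

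The text names no concurrent, historical or external comparison group. Figure 2, which outlines Phase 2, is not shown in the copy reviewed. Whatever it contains, the SAP plans no between-group test.

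**The concern.** Effectiveness is a causal claim: patients did better than they would have done without the intervention. Supporting it needs some estimate of what would have happened otherwise, and a single group measured before and after does not supply one.

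The setting makes this more than a formality. Patients are enrolled around a critical-illness admission, and the intervention starts before discharge, so the baseline is apparently taken in or near an acute episode. (The order of activities in Table 2 implies this; it is not stated outright.) Symptoms and quality of life may then improve as patients recover, or worsen as multimorbidity progresses, whatever the nurse does.

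The plan sets no success criterion, so what is at stake is the stated inference. A report that followed Year 2 Goal 4 and SAP section c as written would present within-person change as evidence of effectiveness on both primary outcomes. The SAP sentence is wider still, since it is not limited to the primary outcomes. The error can run either way: natural improvement can pass for benefit, and natural decline can hide a real one.

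**Working it through.** **Plan's own figure.** There is none to reproduce. The 25 participants come without an alpha, power, effect size, SD or dropout rate. The core argument needs no simulation; the numbers below only show its scale.

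**Inputs from the documents.** 25 participants, all treated (Year 2 Goal 3). Surveys at baseline, 6 weeks and 3 months after completion (Table 2). Wilcoxon signed-rank and Friedman tests with Kendall's W (SAP section c). On the Table 2 wording the last survey falls about 6 + 13 = 19 weeks after discharge. Year 2 Goal 4 lists the time points more briefly, and its 3 months could be read as about 13 weeks. Either interval leaves time for natural change.

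**Assumptions.** Two-sided alpha 0.05; one score per test; normally distributed paired changes; natural change expressed in SD of the change score.

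**Step 1: what the test sees.** Write each patient's change as D = e + r + error, where e is the intervention effect and r the natural change. The mean of D is e + r. Both planned tests use only within-person data, so they respond to the sum and carry no information on the split.

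**Step 2: no intervention effect (e = 0).** Probability that one exact Wilcoxon test is significant. The rejection limits are a smaller rank sum of at most 89 at n = 25 and at most 52 at n = 20, and the exact size is 0.048 for both.

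| Natural change r (SD) | n = 25 | n = 20 |
|---|---|---|
| 0 | 0.048 | 0.048 |
| 0.2 | 0.153 | 0.132 |
| 0.3 | 0.289 | 0.233 |
| 0.5 | 0.645 | 0.541 |
| 0.8 | 0.962 | 0.912 |

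These come from 100,000 simulated trials per cell. As a check, the paired t-test with noncentrality r√n (for example 0.5 × √25 = 2.5) gives 0.161, 0.302, 0.670 and 0.970 at n = 25 for r = 0.2, 0.3, 0.5 and 0.8. That is slightly higher, as expected for normal data.

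**Step 3: different truths, same result (n = 25).**

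| Effect e | Natural change r | Sum | Significant |
|---|---|---|---|
| 0.5 | 0 | 0.5 | 0.645 |
| 0 | 0.5 | 0.5 | 0.647 |
| 0.25 | 0.25 | 0.5 | 0.645 |
| 1.0 | −0.5 | 0.5 | 0.645 |
| 0.5 | −0.3 | 0.2 | 0.152 |
| 0.5 | −0.5 | 0 | 0.049 |

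The first four rows agree within simulation error, although the intervention effect ranges from 0 to 1.0 SD. In the last row a real 0.5 SD benefit is detected no more often than chance.

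**Step 4: Kendall's W.** W = Friedman statistic / [n(k − 1)], which is the statistic divided by 25 × 2 = 50 here. With no change the statistic is roughly chi-square on 2 degrees of freedom, with median 2 ln 2 = 1.39, so median W is about 1.39/50 = 0.03. Now keep e = 0, let natural change be complete by 6 weeks and then stable, and take independent within-person errors (40,000 runs). At n = 25, median W is 0.03, 0.045, 0.13 and 0.27 for r = 0, 0.2, 0.5 and 0.8 SD, and the Friedman test is significant in 0.052, 0.129, 0.567 and 0.937 of trials. If half the change comes by 6 weeks and half later, median W at 0.8 SD is 0.21. Preferring effect sizes to p-values therefore does not avoid the problem.

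**Step 5: does the low-power warning cover it?** No. At r = 0.5 SD and e = 0, moving from 20 to 25 completers raises the chance of significance from 0.541 to 0.645. More patients measure the same confounded sum more precisely.

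**The case against.** The strongest reply concerns weight. The documents call Phase 2 a pre-post pilot and name the comparison in the same sentence as the effectiveness claim. The SAP speaks of exploring, not confirming, and no decision hangs on a p-value. Table 2 lists planning for a later randomised trial, which is where a controlled test belongs. Feasibility and acceptability, which this design can assess, have their own evaluation. On that view only two phrases are at issue. All of this is true, and it keeps the point from being fatal. It does not remove it: naming the design does not limit the conclusion drawn from it, and nothing in the text says that change cannot be attributed to the intervention. If the results feed into planning the randomised trial, an effect size that mixes in natural change could mislead that too.

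It is also fair to say that the percentages rest on assumed natural changes, that median W depends on the assumed time course, and that the absence of a comparator was read from the text without Figure 2. These affect the illustration and the degree of certainty about the layout. The within-person tests in the SAP would still give no comparison between groups.

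**Conclusion.** The concern holds as a fault in the stated inference. Year 2 Goal 4 and SAP section c promise evidence on effectiveness that the planned analysis cannot give. With 25 completers and no intervention effect, the chance that a single Wilcoxon test is significant runs from 5% to 96% as natural change goes from 0 to 0.8 SD; with 20 completers, from 5% to 91%. Those figures assume a two-sided 5% level, normal changes and one score per test. The documents give no size for natural change, so no point in the range can be called likely. The conclusion itself rests only on the single treated group and the within-person tests. It should be corrected before results are reported. The pilot status and the planned randomised trial limit the harm.

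**What to change.** 1. Section 4, Year 2 Goal 4: replace the statement that effectiveness on the primary outcomes will be evaluated with *describe within-person change over time in the primary outcomes*.
2. SAP section c: replace the closing reference to evidence of effectiveness with *to describe within-person change over time in the primary and secondary outcomes*.
3. SAP section c: add *Because there is no control group, change, statistical significance and Kendall's W are not attributed to the intervention.*
4. Report the ESAS and SF-36 changes at 6 weeks and at 3 months after completion with 95% confidence intervals. An estimator that matches the rank tests is preferable, such as the Hodges-Lehmann median change with its signed-rank interval. For scale, the half-width for a mean change is 2.064/√25 = 0.41 SD of change at n = 25 and 2.093/√20 = 0.47 at n = 20. This item is useful, but the correction does not depend on it.

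The sentence on secondary outcomes in Year 2 Goal 4 states an expectation and can stay. Outcomes, tests, sample size and the feasibility and acceptability evaluation are unchanged.

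The cost is two rewordings, one added sentence and an extra column in the results table, with no new patients, data or tests. The one drawback is that the stated claim becomes less favourable.

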# Statistical Analysis Plan

- a. Primary outcome variable.
  - Symptom Burden: Edmonton Symptom Assessment System (ESAS)
  - Quality of Life: BRICS NINR Short Form Survey (SF-36)
- b. Secondary outcome variables.
  - Health-care Utilization: No. of emergency visit, Hospitalizations, Critical care admissions
- c. Statistical plan including sample size justification and interim data analysis.

Data collection and analysis are iterative processes throughout Goal 1, Stages 1-6 of the EBCD process, and Goal 3 and Goal 4 for intervention evaluation. The majority of data collected in phase 1, except the baseline survey, are qualitative and will be analyzed using thematic analysis. The software Atlas ti. will support qualitative analysis.

Quantitative data will be analyzed using descriptive statistics followed by inferential statistics. As a pilot study, the analyses of Phase 2 data will likely not have adequate power to detect significant differences. Therefore, effect sizes, followed by statistical significance will be explored for evidence of the effectiveness of the intervention on outcomes. To compare quantitative data at different time points, we will use Wilcoxon signed rank test to evaluate changes from baseline to 6 weeks and baseline to 3 months post-intervention. Additionally, the changes across baseline, 6 weeks, and 3 months post-intervention will be analyzed using the Friedman test for repeated measures, with Kendall's W employed to assess effect size.

Quantitative analyses will be performed using the Statistical Package for the Social Sciences (SPSS) or equivalent software. We will evaluate the acceptability and feasibility of the intervention using qualitative analysis of interview data from selected participants who attended the intervention, left the intervention if agree to interviewed and the nurse delivering the intervention. The quantitative data from satisfaction and feasibility items will be descriptively analyzed (mean, range, percentages). Further, evaluation of participants' recruitment rate, retention rate and no. of nurse patient interaction will be performed.

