**Table 1: Phase 1**

Goal 1: Develop symptom management toolkit by understanding symptom trajectory, burden, and needs of the patient and family caregivers and key stakeholders' preferences	
Stages/ Goals	Goals and Activities
Stage 1	Project preparation and relationship building - IRB approval - Identify and gain support from the stakeholders to prepare for the stages of research
Stage 2	Collect data from patients and family caregivers' experiences on symptom trajectories and burden via filmed narrative interviews and survey Approximately 12 participants identified and recruited who meet the inclusion criteria Conduct a baseline survey and filmed and/or narrative interviews (narrative in-person or virtual interviews) The baseline survey will include questions on demographics (age, gender, ethnicity, education, and postal code), caregiver type, clinical profiles (co-morbidities, diagnoses, healthcare utilization in the last 3 months), symptom burden, quality of life, pain, fatigue, social support, and resilience. Patient-family shared event to validate findings, agree on quotes from interviews to represent shared patient-family experiences to include in the experience film and identify 3-5 strategies for effective symptom management
Stage 3	Collect data from key-stakeholders (nurses, physicians, researchers, community partners, and other identified stakeholders) experiences and priorities Approximately 12 in-depth filmed and/or narrative interviews (semi-structured in-person or virtual interviews) Non-participants observations of critically ill patients admitted or eligible be admitted at the JHH-IMCU Analysis of data followed by stakeholders' workshops to validate findings and identify 3-5 improvement priorities for symptom management
Stage 4	Co-design event All participants will collaborate in a workshop-style event Patients, family caregivers, and key-stakeholders experiences and improvement priorities shared via film and discussion Symptom trajectory developed in a timeline chart with patients and family experiences since the diagnosis of multimorbidity Facilitated discussion supports the identification of 3-5 shared priorities for the toolkit to reduce symptom burden and improve QOL in multimorbidity

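### Kendall's W is not a usable effect size for the three health-care utilization counts in 25 patients, and any p-values on these counts should be exact

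*Combined protocol and SAP*

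**What the plan says.** Section b of the SAP names one secondary outcome family: "Health-care Utilization: No. of emergency visit, Hospitalizations, Critical care admissions". Section c then sets a single rule for everything quantitative: "To compare quantitative data at different time points, we will use Wilcoxon signed rank test to evaluate changes" from baseline to 6 weeks and from baseline to 3 months. The three time points together get the "Friedman test for repeated measures, with Kendall's W employed to assess effect size".

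The SAP expects low power ("the analyses of Phase 2 data will likely not have adequate power to detect significant differences") and for that reason puts effect size ahead of testing: "effect sizes, followed by statistical significance will be explored for evidence of the effectiveness of the intervention on outcomes".

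Table 2 gives the Phase 2 sample: "Recruitment of 25 participants meeting eligibility criteria". It also says that the baseline survey repeats the Phase 1 measures, and Table 1 asks there for "healthcare utilization in the last 3 months". The intervention begins before discharge, so every Phase 2 patient is in hospital at baseline.

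The documents do not give an event rate, the window covered by each follow-up count, or a rule for ties. They also do not say whether the index admission counts, or whether p-values are exact or large-sample.

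**The concern.** Rank methods suit the questionnaire scores, where most patients will differ between visits. Utilization is a small integer count, and a patient may well have the same count, often zero, at each visit. When that is common, two things happen.

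- **Effect size.** Patients with no change stay in the denominator of W and add nothing to the numerator. W then reflects how rare the event is as well as how consistently it changed.
- **P-values.** The signed-rank test in its standard form sets aside zero differences. The Friedman chi-square is likewise unaffected by fully tied patients. With few patients left, the large-sample approximations are unreliable, and the SAP does not say which version will be used.

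Because the SAP reads effect size first, W would be the headline figure for utilization. Table 2 lists planning of a randomized trial among the outputs, and that planning needs event rates and proportions with intervals. The SAP does not name these for utilization.

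**Working it through.** The sample size of 25 is stated without alpha, power or event rate, so the plan has no figure to reproduce. The steps below check the mechanism.

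**Inputs from the documents:** n = 25; three time points; three event counts; 3-month baseline look-back. **Assumed:** two-sided 0.05 (the SAP sets no alpha), the event rates, and the follow-up windows.

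**1. Cap on W.** Let v_i be patient i's within-patient ranks, centred at their mean. Tie-corrected W = ‖Σv_i‖² / (n Σ‖v_i‖²). A patient with three equal counts has v_i = 0. By Cauchy–Schwarz, W ≤ m/n, where m is the number whose count differs at all.

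Example: 5 of 25 patients have one event at baseline and none later. Each has ranks 3, 1.5, 1.5, which centre to 1, −0.5, −0.5, with squared length 1.5. The sum is (5, −2.5, −2.5), with squared length 37.5. W = 37.5 / (25 × 5 × 1.5) = 0.20, which equals 5/25.

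| Patients changed | Maximum tie-corrected W |
|---|---|
| 4 | 0.16 |
| 5 | 0.20 |
| 6 | 0.24 |
| 10 | 0.40 |
| 20 | 0.80 |

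In 20,000 simulated data sets the bound was never broken. Without tie correction W is lower still (0.03 for 5 changed in the pattern above).

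**2. Signed-rank p-value.** With m equal changes in one direction, exact two-sided p = 2 × 0.5^m. The large-sample statistic without continuity correction is z = √m.

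| Changed | Exact p | Large-sample p |
|---|---|---|
| 4 | 0.125 | 0.046 |
| 5 | 0.0625 | 0.025 |
| 6 | 0.031 | 0.014 |

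**3. Friedman p-value.** In the same pattern chi-square = 2m on 2 degrees of freedom, so p = exp(−m). With 3 changed, p = 0.0498. Under permutation each changed patient's event is equally likely to fall at any of the three times, so the exact p is 3/3³ = 3/27 = 0.111.

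**4. How often few patients change.** Assume independent windows, at most one event per window, and the same event probability p in both. The chance that a patient changes is then q = 2p(1 − p), and the number changed is binomial(25, q).

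| Assumed p per window | Chance that 5 or fewer change |
|---|---|
| 10% | 71% |
| 15% | 36% |
| 20% | 14% |
| 30% | 2% |

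**5. Effect of the index admission.** Poisson counts were simulated with assumed windows of 3 months, 6 weeks and 3 months.

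| Rate per 3 months | Index admission at baseline | Mean W, no effect | Mean W, rate halved |
|---|---|---|---|
| 0.1 | not counted | 0.05 | 0.06 |
| 0.2 | not counted | 0.06 | 0.08 |
| 1.0 | not counted | 0.12 | 0.22 |
| 0.1 | counted | 0.87 | 0.93 |
| 0.2 | counted | 0.78 | 0.88 |
| 1.0 | counted | 0.46 | 0.69 |

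At each rate shown, counting the index stay moves W far more than halving the event rate does. When it is counted, 96% to 100% of patients change and the cap no longer binds.

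**The case against.** The strongest reply is that the premise is not in the documents. A reader might infer that all three counts are mostly zero. No rate is given, and the Background says that multimorbidity goes with higher utilization and that these adults are often hospitalized. At an assumed 30% event rate per window the chance of 5 or fewer changed patients is only 2%. This stands: the cap is a conditional problem, most plausible for critical care admissions.

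A reader might also infer that W discards unchanged patients. It does not; it keeps them in n and is diluted by them. If 20 of 25 patients did not change, a low W is a fair statement about concordance across the sample. Setting aside zero differences is also standard signed-rank practice and does not make the test invalid. Both points stand. What remains is that W cannot show the size of a change in event counts, and the SAP relies on it as the effect size.

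Nor can the point be separated from the baseline window. If the index stay counts, no baseline hospitalization count is zero and the problem reverses. This corrects the scope but does not rescue W, which is then large with no intervention effect.

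Finally, the SAP promises descriptive statistics before inference, does not prescribe large-sample p-values, and places significance second. The Objectives list four other secondary outcomes. These facts lower the priority, but they do not supply a suitable summary for the counts.

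**Conclusion.** The point holds in a conditional form. As written, the SAP applies signed-rank, Friedman and Kendall's W to the utilization counts by default. If few counts change, W is capped at the share that changed (0.20 for complete elimination of an event in 5 of 25), and large-sample p-values can cross 0.05 when exact ones do not: at 4 and 5 changed for signed-rank, and at 3 for Friedman. If the index admission is counted, mean W for hospitalizations is about 0.46 to 0.87 with no effect. For critical care admissions the same would follow only if the intermediate care stay is classed as one. In neither case is W usable as the effect size.

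The algebra and the exact p-values are certain for the patterns shown. The event rates, follow-up windows, Poisson model and 0.05 threshold are assumptions. The documents do not support saying that utilization results will be wrong, only that the stated summary can mislead in either direction depending on facts left open. Priority is minor.

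**What to change.** Amend the SAP for the three utilization counts only:

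- Do not use Kendall's W as the effect size.
- State the window of each count and exclude the index admission from the baseline count. A rate per patient-month adjusts for unequal windows but not for the index stay.
- For each window, report the number and proportion with at least one event with an exact 95% interval, events per patient-month, and the number of patients whose count rose, fell or stayed the same. Exact intervals at n = 25 will be wide: 2/25 gives 1% to 26%, 5/25 gives 7% to 41%, and 8/25 gives 15% to 54%.
- Require exact p-values for any signed-rank, Friedman or McNemar test on these counts. State that no exact pairwise test can reach two-sided 0.05 with 5 or fewer changed patients; exact McNemar has the same floor as exact signed-rank.
- Do not use a percentile bootstrap interval for the mean change when few patients change. With 4 of 25 changed it runs from −0.32 to −0.04, and with 5 of 25 from −0.36 to −0.04. Both exclude zero although the exact p-values are 0.125 and 0.0625.

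Keep the rank tests for the questionnaire scores.

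The cost is SAP wording and a few lines of output, plus a check that the survey can separate the index stay from earlier admissions. Utilization will no longer share an effect-size scale with the questionnaires, and some p-values will be less favourable.

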### **4. Study Procedures**

The proposed mixed method study will be conducted in two phases using social (justice)/human centered design. The first phase (Year 1) will empirically describe the prevalence and burden of symptoms from the perspective of patients, family caregivers, health professionals and other stakeholders. Using participatory co-design methodology, EBCD, we will develop a symptom

management toolkit. This approach will identify care delivery and care transitioning preferences and needs of patients with multimorbidity, family caregivers, healthcare providers, and other stakeholders. In the second phase, (Year 2) the data from phase one will inform the refinement and evaluation of a patient-centered symptom management intervention using a pre-post quasi-experimental design.

**Phase 1:** A collaborative study will be implemented to describe the symptom trajectory and burden including pain and fatigue and develop symptom management toolkit for critically ill adults with multimorbidity.

*Year 1, Goal 1:* Develop multimorbidity management (which includes symptom management) toolkit, using co-design, by understanding disease trajectories, symptom trajectory, burden, gender roles and needs of the patient and family caregivers and key stakeholders' priorities. To achieve goal 1 we will use the EBCD and follow its six-stage process (Table 1), using online EBCD toolkit for consistency in documentation and processes. We will work with patients, family caregivers, healthcare providers, and other stakeholders through iterative rounds of data collection, analysis, validation and development strategies to address symptom burden. EBCD takes typically 9-12 months to complete and is proven means for understanding how to make the best use of data about patient, family, and healthcare providers' experience to improve the quality of care and culture of health services. Table 1 details the activities required for each stage of the EBCD process.

[figure not shown]

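### Raw Kendall's W, the only effect size the SAP names, is biased upward by (1 − true W)/n; the bias matters most for small effects and few completers

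*Combined protocol and SAP*

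**What the plan says.** Section c of the Statistical Analysis Plan states that "the analyses of Phase 2 data will likely not have adequate power to detect significant differences". It concludes that "effect sizes, followed by statistical significance will be explored for evidence of the effectiveness of the intervention on outcomes".

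Two analyses of the repeated measures follow. Wilcoxon signed rank tests compare baseline with each follow-up, and no effect size is named for them. In addition, the changes over all three time points will be "analyzed using the Friedman test for repeated measures, with Kendall's W employed to assess effect size".

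Table 2 (Goal 3) gives the sample size: "Recruitment of 25 participants meeting eligibility criteria". Section 4 describes the design as "evaluation of a patient-centered symptom management intervention using a pre-post quasi-experimental design".

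The documents give no bias correction, confidence interval, reference value or benchmark for W. They state no rule for missing surveys and assume no drop-out; retention appears only as a feasibility measure ("recruitment rate, retention rate and no. of nurse patient interaction will be performed").

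**The concern.** W is a rescaled Friedman chi-square and cannot be negative. Chance differences between the visit rank sums therefore always push it upward, and in small samples that contribution is not negligible. The p-value allows for this; W read alone does not.

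The order of evidence makes this relevant. The plan puts effect sizes ahead of significance because it expects the tests to be weak. If W is then taken at face value, part of what is read as effect is an artefact of the number of patients. That share is largest when the true change is small and few patients complete all three surveys. Table 2 also lists planning of a randomised trial among the follow-on activities, so an inflated figure could carry over into that planning.

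**Working it through.** **Inputs.**
- k = 3 time points (SAP, section c).
- n is at most 25 (Table 2). The Friedman test needs all three values from a patient, so n is the number of complete cases. The documents give no drop-out figure; n = 20 and n = 15 are assumptions.
- The plan states no power, expected effect or expected W, so it has no figure of its own to reproduce. The shifts of 0.3, 0.5 and 0.8 SD and the correlation of 0.5 below are assumptions.

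**Step 1: no systematic change.** W = χ²/[n(k − 1)], where χ² is the Friedman statistic. Under no systematic change χ² has mean k − 1, so

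mean W = (k − 1)/[n(k − 1)] = 1/n.

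This gives 1/25 = 0.040, 1/20 = 0.050 and 1/15 = 0.067. Simulation of 40,000 trials per n gave 0.040, 0.050 and 0.066, with practically the same values for tied scores and for unequal correlations between visits.

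**Step 2: a real change.** Without ties, W = [1 + (n − 1)r]/n, where r is the mean rank correlation between pairs of patients. The expected value of r is the true W, so

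mean W = true W + (1 − true W)/n.

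**Step 3: true W for the assumed shifts.** Take normal scores with SD 1 and correlation 0.5, shifted by d SD at both follow-ups. The difference between two visits has SD √(2 − 2 × 0.5) = 1, so a patient's baseline outranks a given follow-up with probability Φ(d). Write a = Φ(d) − 0.5. The mean ranks differ from 2 by 2a, −a and −a. The ranks 1, 2, 3 have sum of squares 2 about their mean, so true W = (4a² + a² + a²)/2 = 3a².
- d = 0.3: a = 0.118, true W = 0.042
- d = 0.5: a = 0.191, true W = 0.110
- d = 0.8: a = 0.288, true W = 0.249

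**Step 4: mean raw W.**

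| Shift | True W | n = 25, formula | n = 25, simulated | Ratio | n = 15, formula | Ratio |
|---|---|---|---|---|---|---|
| 0.3 SD | 0.042 | 0.042 + 0.958/25 = 0.080 | 0.080 | 1.9 | 0.042 + 0.958/15 = 0.106 | 2.5 |
| 0.5 SD | 0.110 | 0.110 + 0.890/25 = 0.146 | 0.146 | 1.3 | 0.110 + 0.890/15 = 0.169 | 1.5 |
| 0.8 SD | 0.249 | 0.249 + 0.751/25 = 0.279 | 0.280 | 1.1 | 0.249 + 0.751/15 = 0.299 | 1.2 |

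The absolute bias at n = 25 is 0.03 to 0.04 throughout. The ratio is large only where true W is small.

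**Step 5: the correction.** Solving step 2 for true W gives (nW − 1)/(n − 1). Its simulated mean under no change lies between −0.0007 and 0.0002 for n from 8 to 25. At 0.3 and 0.5 SD it averages about 0.042 and 0.110.

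**Step 6: p-values.** Simulated rejection by the Friedman test at the 5% level, under no change, was 4.5% to 5.6%. The test is sound.

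**The case against.** The strongest reply is that the accompanying test already shows how much could be chance. With two degrees of freedom p = exp(−χ²/2). W = 0.10 (an illustrative value; the plan sets no cut-off) means χ² = 5 and p = 0.08 at n = 25, and χ² = 3 and p = 0.22 at n = 15. Anyone who reads W beside its p-value is protected. That stands, and it limits the point to W as a measure of size. It does not remove the point, because the plan puts size ahead of significance.

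Three further objections stand in part.
- The SAP speaks of effect sizes in the plural, and W enters only through the additional Friedman analysis. W is the only one named, but the plan does not say that it alone decides.
- The bias is smaller than the sampling noise. At n = 25 and 0.5 SD the bias is about 0.036 and the SD of W is 0.089. Root mean squared error is about 0.096 raw and 0.093 corrected, so the correction removes bias but adds little precision.
- The correction says nothing about benefit. W has no direction and the pre-post design has no stated control group.

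A reader might also infer more than the documents support:
- That W will show an effect in this trial, or must grow as patients leave. Both hold only on average. When null trials of 25 lost patients at random, W rose in 62% of them with 20 left and in 68% with 15 left; in the rest it did not rise.
- That the plan will rank outcomes or subsets by W. It states no such comparison, and the measures are collected in one survey per time point, so numbers of completers may well be similar across outcomes.
- That poor retention is to be expected. No passage gives a figure.

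**Conclusion.** The point holds as a bias in the size of W. It is exact algebra when there are no ties, and simulation with tied scores gave nearly the same null means. It does not call the planned tests into question.

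With all 25 patients and no systematic change the bias is a modest 0.04. It is comparable to the signal itself for a small effect (true W 0.042 at an assumed 0.3 SD shift) and falls to about 12% of the true value at 0.8 SD. Fewer completers make it larger, but how many there will be is not known from the documents. No systematic change here means no shift in the group; if every patient's scores were identical at all visits, W would be undefined.

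For an exploratory pilot this is a reporting correction worth making because it costs almost nothing.

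**What to change.** In section c of the SAP, after the sentence on the Friedman test, state that for each outcome the report will give:
- raw W;
- the bias-corrected value (nW − 1)/(n − 1);
- n, the number of patients with all three surveys;
- the Friedman p-value.

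State that effect size will be judged on the corrected value.

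**Cost.** One sentence and one formula, worked from W and n, which the planned analysis already yields. No new data and no change of design.

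**What the team should expect.** The reported effect size will be smaller. It will often be negative when there is little or no change: in about 61% of null trials at n = 25, and in about 31% at a true 0.3 SD shift. A negative value should be read as no evidence of change. The SAP should not describe the corrected value as the mean rank correlation between patients, since that identity fails when scores tie, as symptom ratings and visit counts readily may. Direction has to come from elsewhere, for example a signed effect size for each comparison with baseline.
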